## 9.3 Analysis

### 9.3.1 Statistical hypotheses

All statistical tests will be two-sided at the 5% overall alpha risk level. All Confidence Intervals (CIs) will be two-sided and presented at the 95% confidence level. No alpha risk adjustment is planned.

### 9.3.2 Population for analyses

The following analysis population will be considered:

- Included Set (IS): This set corresponds to all patients included for the study and with an Informed Consent Form (ICF) signed.
- Analysis Set (AS): This set corresponds to all patients from the IS with at least one follow-up visit (i.e. with at least a date of visit completed for visits V1, V2, V3).

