#### **4.4.2 Study setting**

The GP examines the patient and makes the diagnosis of CVD, based on clinical signs and symptoms. Patients who receive a diagnosis of CVD according to international guidelines who require conservative or invasive treatment can be included in the study. Duplex ultrasound or any other specific examination is not required to make the diagnosis, but could be done if needed according to routine clinical practice and recommendations. Each participating GP (120 GPs) will select approximately between 10 and 15 patients with CVD.

During the inclusion visit (V0), a treatment strategy will be proposed to the patient with confirmed CVD by the GP. The treatment can be conservative or invasive, depending on the severity of the disease. Patients awaiting invasive treatment may receive conservative treatment to alleviate symptoms. The choice of treatment modality is left to the discretion of the treating physician, in agreement with the patient and according to local policies. As this is an observational study, there will be no interference in the choice of treatment, and no restrictions will be imposed.

Commonly proposed conservative treatment options include compression therapy, and oral or topical venoactive drugs. If the GP decides that the patient needs an invasive treatment, then the patient will be referred to a venous centre. The specialist to whom the patient is referred, chooses the type of invasive treatment, as done in standard clinical care. The specialist may also prescribe conservative treatment to the patient, either while awaiting invasive treatment or in case invasive treatment is not deemed necessary.

[figure not shown]
Patients and their GP may decide to switch at any time between conservative treatments or to undergo an intervention as secondary/add-on treatment to conservative treatment.

Baseline data will be collected by the GP on the day of the V0. Follow-up visits, which are expected to take place within the scope of routine clinical practice, will be organized by the GP at defined timepoints after the V0: at 6 weeks, 12 weeks, 6 months, 12 months and 24 months of follow-up (V1-V5).

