A delay between referral to the venous centre during the V0 and the day of invasive treatment is anticipated. To allow assessment of the primary study objective, GPs will be asked to invite the patients for a follow-up visit 12 weeks after the invasive treatment took place (V-i), provided that it falls within the scope of routine medical practice in terms of visit frequency.

Due to the real-world setting, patients might not be assessed exactly at the proposed weeks/months. Therefore, some visits may not take place if they are not within the scope of regular medical practice. Additionally, a time range around the visits will be allowed. The frequency of follow-up visits is upon the discretion of the treating physicians.

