**4.6 Study Flowchart**

**Table 1. Schedule of assessments**

| Visits                       | V0                      | V1     | V2      | V3      | V4       | V5       | V-i a                  |
|------------------------------|-------------------------|--------|---------|---------|----------|----------|-----------------------------------|
|                              | Inclusion visit (Day 0) | Week 6 | Week 12 | Month 6 | Month 12 | Month 24 | 12 weeks after invasive treatment |
| Informed consent             | X                       |        |         |         |          |          |                                   |
| Inclusion/exclusion criteria | X                       |        |         |         |          |          |                                   |

|  |                |   |   |   |   |   |   |
|--|----------------|---|---|---|---|---|---|
| Patient characteristics b   | X              |   |   |   |   |   |   |
| Risk factors   | X              | X | X | X | X | X | X |
| Treatment characteristics
(type/day of treatment
initiation)                                 | X c | X | X | X | X | X | X |
| Conservative treatment
compliance   |                | X | X | X | X | X | X |
| Concomitant treatment  | X              | X | X | X | X | X | X |
| Treatment changed since
last visit/intervention as
secondary treatment or
re-intervention |                | X | X | X | X | X | X |
| CIVIQ-20 d  | X              | X | X | X | X | X | X |
| CEAP   | X              | X | X | X | X | X | X |
| rVCSS  | X              | X | X | X | X | X | X |
| Symptomatology d  | X              | X | X | X | X | X | X |
| Satisfaction d  |                | X | X | X | X | X | X |
| AEs  |                | X | X | X | X | X | X |
| Study discontinuation  |                | X | X | X | X | X | X |

AEs: Adverse Events, CEAP: Clinical Etiological Anatomic Pathophysiologic classification, CIVIQ-20: Chronic Venous Insufficiency Quality of life questionnaire, V: Visit, rVCSS: revised Venous Clinical Severity Score

a If the V-i overlaps with another visit (V1-V5) then it will replace this visit.

b Patient characteristics include demographics, type of occupational activity, clinical characteristics, history of CVD, treatment history, specific comorbidities.

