# 7. Assessment of effectiveness

The primary outcome is the patients' QoL, related to the CVD. The CIVIQ-20 (Chronic Venous Insufficiency quality of life Questionnaire) considers CVD as a whole (Launois 2010, Vuylsteke 2015). It is a reliable, valid, and sensitive instrument applicable to international studies of patients with CVD. The maximal score is 100, with a high score corresponding to lower patient comfort. In order to calculate the GIS, the difference between the final score and the minimum possible score is to be divided by the difference between the theoretical maximum and minimum scores ( $100-20=80$ ), multiplied by 100.

For the primary endpoint, the CIVIQ-20 score will be collected at V0, and at V2 (12-weeks after V0) for the conservative treatment group and at V-i (12 weeks after the day of invasive treatment) for the invasive treatment group.

The secondary outcomes are:

1. Patient characteristics at V0 as described in [Section 6.1 By visit](#).
2. Treatment characteristics as described [Section 6.1 By visit](#).
3. The **CIVIQ-20** GIS, as described above for the primary outcome.

4. The **CEAP** classification, which is the worldwide standard for describing the clinical features of CVD. In this survey, we only use the C-classification. It is a scale from 0 (C0) to 6 (C6), with a higher score representing more severe disease. However, as a descriptive instrument, the CEAP classification responds poorly to change.
5. The **VCSS** was developed in 2000 and adapted in 2010 (r-VCSS) ([Rutherford 2000](#), [Vasquez 2010](#)). The r-VCSS is an evaluative instrument that is responsive to changes in disease severity over time and in response to treatment. It includes 10 items, each scored on a severity scale from 0 to 3 (maximal score: 30; a higher score representing more severe disease). It enables longitudinal outcomes assessment.
6. Patients will evaluate CVD related **symptoms** using a Visual Analogue Scale (VAS) varying from 0 to 10. Symptoms include: having heavy legs, having pain in the legs, sensation of swelling, having night cramps, itching [leg], sensation of burning, sensation of pins and needles, restless legs. This list of symptoms has been validated by the SYM VEIN consensus statement ([Perrin 2016](#)). The final list of symptoms will be defined in the eCRF.

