### **Primary endpoint**

The analyses will be conducted in the AS.

To evaluate the change in the CIVIQ-20 GIS from V0 to a visit realized 12 weeks after the beginning of the treatment (or day of the intervention for patients in the invasive group) in each treatment group, we will compare the V0 value with the value at 12 weeks with a paired t-test or Wilcoxon signed-rank test depending on the distribution of GIS of CIVIQ-20 in each treatment group.

A mixed model could be conducted, with the GIS of CIVIQ-20 as the dependent variable, the visit as a fixed effect and time between V0 and the day of the intervention as covariate and paired on the patient in the invasive group.

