### **Secondary endpoints**

The analyses will be conducted in the AS, overall and by treatment group (conservative group, invasive group). Descriptive statistics and within-group comparative analyses could be done by subgroup of conservative treatment (venoactive drugs, compression, combination of both), or by subgroup of invasive treatment (sclerotherapy, foam sclerotherapy, surgery, thermal ablation (laser or radiofrequency), non-thermal ablation, and venous stenting), if relevant.

Descriptive statistics will be provided for patient characteristics at V0 (in terms of demographics, profession, clinical characteristics, personal and family history of CVD, treatment history, specific comorbidities), risk factors, concomitant treatment and description of treatment characteristics per visit in terms of type of treatment (initial referral from GP and whether they actually received the treatment), concomitant treatment, compliance (for conservative treatment group only).

The proportion of patients who received an intervention as secondary/add-on treatment to conservative treatment (in the conservative treatment group) and the proportion of patients who received a re-intervention (in the invasive treatment group) and number of re-interventions will be provided. If there is enough recurrence (minimum 20% of concerned patients), a Kaplan-Meier analysis could be considered. Time to event will be calculated from the start date of conservative treatment to the date of the secondary/add-on intervention in the conservative treatment group.

Time-to-re-intervention will be calculated from the date of the intervention to the date of the re-intervention in the invasive treatment group.

Patients who will reach the end of the study without receiving an intervention (in the conservative group) or a re-intervention (in the invasive treatment group) will have the time to event censored at the date of treatment discontinuation for any other cause (in the conservative group) or at the date of the end of the study if study ended (in conservative and invasive treatment group).

The change in the CIVIQ-20 GIS over time from V0 to each follow-up visit will be evaluated with the same methods as the primary endpoint.

The change in the clinical part of the CEAP classification over time from V0 to each follow-up visit will be described.

The change in the rVCSS over time from V0 to each follow-up visit will be evaluated with the same methods as the primary endpoint.

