The change in the symptomatology over time from V0 to each follow-up visit will be evaluated with the same methods as the primary endpoints.

The satisfaction score over time from V1 to each follow-up visit will be described as a quantitative variable.

Number and proportion of patients with AEs will be described.

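### The Analysis Set is limited to patients with a dated V1, V2 or V3, so an invasive patient with a valid primary-outcome visit (V-i) can fall outside the primary analysis

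*Protocol*

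**What the plan says.** Section 9.3.2 takes into the AS those members of the Included Set "with at least one follow-up visit (i.e. with at least a date of visit completed for visits V1, V2, V3". The first half of that phrase is general. The part after the i.e. names three visits only.

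The AS is the population for everything that follows. Under Primary endpoint in section 9.3.3: "The analyses will be conducted in the AS". Under Secondary endpoints: "The analyses will be conducted in the AS, overall and by treatment group (conservative group, invasive group". The adverse-event summary belongs to that same block ("Number and proportion of patients with AEs will be described"), and no separate safety set is defined.

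Section 7 collects the primary CIVIQ-20 value at V2 for the conservative group and "at V-i (12 weeks after the day of invasive treatment) for the invasive treatment group". Section 4.4.2 describes V-i as a follow-up visit with the GP, additional to the scheduled ones "at 6 weeks, 12 weeks, 6 months, 12 months and 24 months of follow-up (V1-V5"). It also warns that "some visits may not take place if they are not within the scope of regular medical practice". Footnote a of Table 1, repeated in section 6.1, adds: "If the V-i overlaps with another visit (V1-V5) then it will replace this visit".

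**The concern.** A primary analysis population should not shut out patients who have the primary outcome. Here the visit that carries the outcome in the conservative group (V2) is on the qualifying list, and the visit that carries it in the invasive group (V-i) is not. Whether an invasive patient enters the primary analysis therefore depends on attendance at a different visit from the one at which the outcome was measured.

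The omission of V4 and V5 is a second consequence of the same phrase and touches both groups. Table 1 and section 8.1 have adverse events assessed at every follow-up visit. A patient whose only follow-up contact is at month 12 or 24 has those data collected, yet is left out of the AS-based summaries of secondary endpoints and adverse events.

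**Working it through.** The protocol states no figure for this point, and the sample-size numbers do not enter into it. The check is mainly a comparison of rules.

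**Step 1: apply the literal rule to each visit pattern.** Inputs: AS definition (9.3.2), primary visit by group (7), overlap rule (Table 1 footnote a).

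| Group and visits with data | Value at the group's primary visit? | In the AS as written? |
|---|---|---|
| Conservative: V0, V2 | yes | yes |
| Invasive: V0, any of V1-V3, V-i | yes | yes |
| Invasive: V0, V-i only | yes | no |
| Invasive: V0, V-i, V4 and/or V5 | yes | no |
| Invasive: V0, V-i replacing V3, no V1 or V2 | yes | not determined by the text |
| Either group: V0, V4 and/or V5 only | no | no |

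Rows 3 and 4 are the primary-endpoint problem. Row 6 is the problem for secondary endpoints and adverse events. By the general half of the sentence every row would qualify, so the i.e. contradicts the criterion it is meant to explain.

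**Step 2: where V-i falls.** With a wait of w weeks from V0 to the intervention, V-i is due at week w + 12. It cannot fall at week 6 (V1) on schedule, and it falls at week 12 (V2) only if w is close to 0. Taking month 6 as about week 26, it falls on V3 when w is about 26 - 12 = 14. For waits of that length or more, V1 (week 6) and V2 (week 12) both precede the intervention. Entry to the AS then rests largely on GP visits made before treatment.

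**Step 3: size, illustration only.** Assume that each of V1, V2 and V3 is attended with probability a, independently of the others and of V-i, and that V-i overlaps none of them. The share of V-i completers with no dated V1-V3 is (1 - a)^3:

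- a = 0.75: 0.25^3 = 0.016, about 2%
- a = 0.50: 0.50^3 = 0.125, about 13%

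The protocol gives neither a nor the independence. Missed visits may cluster in the same patients, which would raise the share. Patients who return for V-i may be good attenders in general, which would lower it.

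**The case against.** The strongest reply is that the sentence partly cures itself. Its leading criterion is any one follow-up visit, section 4.4.2 calls V-i a follow-up visit, and a sensible programmer might apply the general half. That stands as a reason to call this an inconsistency within one sentence. It does not repair it, because the i.e. is the operative definition. Section 9.3.3 leaves the rules for treatment groups and for missing CIVIQ-20 scores to the SAP, but 9.3.2 fixes the AS itself, so a SAP that follows the protocol inherits the restriction.

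A second reply is that few patients may be affected. V1-V5 apply to everyone. The intervention date is collected retrospectively at a later visit, and the GP needs that date to time V-i, so an earlier GP contact, often one of V1-V3, is a natural source. A specialist's letter is another possible source. This lowers the expected number without removing the problem.

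Three stronger readings are tempting and are not supported:

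- *A reader might infer from footnote a that an overlapping V-i deletes a qualifying date.* On that reading only two qualifying visits remain, and the share becomes (1 - a)^2, or 6% at a = 0.75 and 25% at a = 0.50. The footnote can equally mean that V-i fills the slot of the visit it replaces, in which case an overlapping patient qualifies. The protocol does not say which date is entered. By step 2, V3 is also the only realistic overlap among V1-V3.
- *A reader might infer a selective loss that biases the result.* No direction or effect on the change score can be shown from the protocol. The analyses are described as mainly descriptive, and the primary test is a before/after comparison within each group.
- *A reader might infer that adverse events are lost.* They are still recorded in the eCRF, and usual pharmacovigilance reporting applies. They would be absent only from the AS-based summary.

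**Conclusion.** The AS definition is wrong as written. Followed literally, it excludes invasive patients who have a valid V0 and V-i pair, while no conservative patient with the primary V2 value can be excluded in the same way. It also excludes patients of either group first seen at V4 or V5 from the secondary and adverse-event summaries. Nothing elsewhere in the protocol corrects this. Whether the overlap rule adds to the exclusions is left open by the text.

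The number of patients is unknown and may be small. The 2% to 13% of V-i completers rests on assumed attendance of 0.75 to 0.50 per visit, independence and no overlap, none of which comes from the protocol. The point does not depend on that range, because it concerns a stated rule that conflicts with the stated primary visit. It is a wording correction of moderate weight that should be made before database lock, since all the data concerned are collected in any case.

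**What to change.** In section 9.3.2, define the AS as all patients of the Included Set with at least one dated follow-up visit among V1-V5 or V-i. Add one sentence saying that a V-i which replaces a scheduled visit also counts as that visit, so that the treatment of overlaps is settled. The adverse-event summary can then stay in this AS, and no separate safety set is needed.

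The cost is one or two lines in the protocol and a matching population flag in the SAP. Visits, patient burden, data collection and the sample size do not change. The change should be made before database lock, because altering the primary population afterwards could look data-driven.

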### 9.3.3 Statistical Analysis

#### General considerations

The SAP, developed and finalized before the study database lock, will include a description of the statistical methods, analyses planned, and planned tables and figures, in accordance with the objectives of the protocol.

The analyses will be mainly descriptive, and all information will be reported in summary tables. Summary data will be provided for all variables collected and will be done by treatment group (conservative group, invasive group) and overall. Details on rules defining groups will be provided in the SAP. Descriptive statistics could be done by subgroup of conservative treatment (venoactive drugs, compression, combination of both), or by subgroup of invasive treatment (sclerotherapy, foam sclerotherapy, surgery, thermal ablation (laser or radiofrequency), non-thermal ablation, and venous stenting). Any additional subgroup analyses will be defined in the SAP.

Unless specified, missing data will not be imputed and all analyses will be based on observed case. Rules for handling missing score of CIVIQ-20 will be detailed in the SAP. To minimise the number of missing data, a specific query will be generated (automatic or manual) in order to confirm the data are missing and not forgotten in the eCRF.

The statistical package SAS® v.9.4 will be used to perform all statistical analyses.

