### **9.2 Sample size**

Considering a Minimum Clinically Important Difference (MCID) of 5 points before/after treatment for the primary endpoint (CIVIQ-20 GIS), a default correlation of 0.5, and with an expected drop-out of 60% of patients in the conservative group and 25% in the invasive group, we propose the recruitment of 1650 patients (safe margin), to finally include minimally 1590 patients (power 90%).

Each investigator (120 GPs) will recruit approximately between 10 and 15 consecutive patients.

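### With 60% (conservative) and 25% (invasive) drop-out planned, the observed-case paired primary test describes only patients who return at 12 weeks; a model using all visits should be the primary estimate

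*Protocol*

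**What the plan says.** - **Expected loss.** Section 9.2 sizes the study for a 5-point before/after MCID on the CIVIQ-20 GIS, "with an expected drop-out of 60% of patients in the conservative group and 25% in the invasive group". It does not say at which time point the loss is counted.
- **Primary test.** Section 9.3.3, Primary endpoint, for the two groups separately: "we will compare the V0 value with the value at 12 weeks with a paired t-test or Wilcoxon signed-rank test". Which of the two is used rests on how the GIS is distributed. The population is the Analysis Set (AS), which section 9.3.2 limits to included patients with at least one of V1, V2 or V3.
- **Missing data.** Section 9.3.3, General considerations: "Unless specified, missing data will not be imputed and all analyses will be based on observed case". The next sentence leaves the rules for a missing CIVIQ-20 score to the SAP.
- **Model.** Under Primary endpoint a mixed model is optional and is described for the invasive group. Under Within-group comparisons, a random-intercept mixed model is one of three general options for continuous variables.
- **Visits.** Section 4.4.2 warns that "some visits may not take place if they are not within the scope of regular medical practice" and leaves visit frequency to the treating physician. The invitation to V-i carries the same condition of routine practice.
- **Attrition bias.** Section 9.1 acknowledges it and names efforts to contact lost patients as the remedy. Section 9.3.3 adds data queries to confirm that missing values are truly missing. No sensitivity analysis for missing data is named.
- **Data available.** Table 1 schedules the CIVIQ-20 at V0, V1 to V5 and V-i.

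**The concern.** The primary objective concerns patients who underwent conservative or invasive treatment. A paired test answers it only for those with both a V0 and a 12-week GIS. If the planning figure applies at 12 weeks, that is about 40% of the conservative group and 75% of the invasive group.

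The loss cannot safely be called random. A patient is seen when routine care calls for a visit, and that may depend on how the patient is doing. Those with persisting complaints may come back more often, or those who are disappointed may stay away. The GIS values at other visits carry information about a missing 12-week value, yet they play no part in the primary test.

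The loss fractions also differ between groups. The same gap between returners and non-returners therefore shifts the two groups' results by different amounts. The protocol tabulates the groups side by side and aims to describe how treatments are associated with outcomes, so this matters even without a formal between-group test.

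**Working it through.** **Inputs from the protocol (sections 9.2 and 9.3.1).** Loss d = 0.60 (conservative) and 0.25 (invasive); MCID 5 points; "a default correlation of 0.5"; power 90%; two-sided alpha 5%; minimum 1590 patients. Not given: the SD of the GIS, the split between groups, and the change in non-returners. These are assumptions below. Change is written as improvement, so positive is better.

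**1. The plan's own figure.** With correlation 0.5, SD of change = SD × √(2 × (1 − 0.5)) = SD. The paired formula is n = ((1.960 + 1.282) × SD / 5)² completers per group, and the total to include is n/0.40 + n/0.75.

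| Assumed SD | Completers per group | Total |
|---|---|---|
| 15 | 95 | 365 |
| 20 | 169 | 649 |
| 25 | 263 | 1009 |
| 30 | 379 | 1454 |

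The figure of 1590 cannot be reproduced without the SD and the split. With equal completers per group it implies 1590 / (1/0.40 + 1/0.75) = about 415 per group and an SD of change of about 31.4. The loss figures thus enter as an inflation of the sample size. That protects power but not against bias.

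**2. Size of the bias.** Let R be the mean change in returners and M the mean change in non-returners. The full-group mean is (1 − d)R + dM, and the paired test estimates R. So

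bias = R − [(1 − d)R + dM] = d × (R − M).

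| Assumed gap R − M | Conservative (0.60) | Invasive (0.25) |
|---|---|---|
| 2.5 | 1.5 | 0.625 |
| 5 | 3.0 | 1.25 |
| 10 | 6.0 | 2.5 |
| 20 | 12.0 | 5.0 |

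A negative gap gives the same sizes with the opposite sign. The bias equals the 5-point MCID at a gap of 5/0.60 = 8.33 points (conservative) or 5/0.25 = 20 points (invasive). If conservative returners improve by 5 points and non-returners by 0, the full-group mean is 0.40 × 5 = 2.0 and the bias is 3.0.

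**3. The same question as a correlation.** Under a normal selection model with correlation r between returning and improving, the conservative bias is r × SD of change × 0.3863/0.40 = 0.966 × r × SD of change. It reaches 5 points at r = 0.35, 0.26 and 0.21 for an assumed SD of change of 15, 20 and 25.

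**4. Effect of a 3-point bias on the test.** Suppose the true mean change is 0. The chance of a significant result in the direction of the bias is Φ(3/SE − 1.96), with SE = SD of change/√n. Take n = 318 (half of 1590 conservative, 40% returning) or n = 415 (step 1).

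| Assumed SD of change | n = 318 | n = 415 |
|---|---|---|
| 15 | 95% | 98% |
| 20 | 76% | 86% |
| 25 | 57% | 69% |
| 31.4 | 40% | 49% |

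The nominal chance in that direction is 2.5%. A bias below the MCID can therefore still decide the test.

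**The case against.** **Missing-score rules are left to the SAP, and observed case is only a default.** True, and whole-score handling there is not excluded, although the sentence may mean only single missing items. But the paired test and the AS are fixed in the protocol. Unless the SAP departs from them, the primary result rests on patients with both values.

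**The protocol does offer a mixed model.** It lists one as a general within-group option and as an optional analysis in the invasive group. Neither is the stated primary analysis in the conservative group, where the planned loss is largest.

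**A reader might infer that the bias exceeds the MCID.** The documents do not support that. It needs a gap above 8.33 points in the conservative group or above 20 in the invasive group, and the protocol says nothing about change in non-returners. Nor does it support a claim that the result is too favourable: patients who improve may be the ones who stop attending.

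**The 60% may not be a 12-week figure.** This stands. Its place in the primary-endpoint sample size points to 12 weeks. If it is the 24-month loss, the loss at 12 weeks and the bias for a given gap would be smaller.

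**The analyses are mainly descriptive, and the other GIS values are not discarded.** Both are correct. No between-group test is planned, and change from V0 to each visit is a secondary endpoint. The values are unused only in the primary test. That limits the harm from unequal distortion, but not the bias within each group.

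**Conclusion.** The point holds as a should-fix. As written, the primary result describes patients who return for the 12-week visit. It estimates the mean change in the treated group without bias only if returning is unrelated to change. The bias is 0.60 (conservative) or 0.25 (invasive) times the gap between returners and non-returners, which for an assumed 5-point gap is 3.0 and 1.25 points. The identity is exact. The gap, its sign, the SD and the group split are assumptions, and the loss fractions are taken to apply at 12 weeks.

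**What to change.** 1. In each group, take the primary 12-week change from a likelihood-based repeated-measures model on all available GIS values. Include every patient with a V0 GIS, not only the AS. Use V0 predictors of loss (C class, rVCSS, age, sex) as covariates.
2. In the invasive group, define time from the intervention and separate pre-intervention from post-intervention values. V1 to V5 run from V0 while V-i runs from the intervention, so pooling them by visit label would mix treated and untreated time.
3. Keep the paired test as a supportive analysis.
4. Add a delta (tipping-point) analysis: worsen the assumed change in non-returners step by step until the conclusion changes. With d = 0.60, a 5-point group estimate falls to 0 at a delta of 5/0.60 = 8.3 points.
5. Tabulate V0 characteristics of patients with and without a 12-week GIS.
6. State the time point to which the 60% and 25% apply.

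**Cost.** No new data are needed. The work is protocol and SAP wording plus programming, with real care over timing in the invasive group. The model relies on missing-at-random, which is why the delta analysis is needed. For patients with no follow-up GIS it can add only what their V0 data predict. The headline is less simple than a paired mean difference.
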